9.1 Study Design

An observational cross-sectional study based on primary data collection is planned in a number of EU countries after the introduction of the OBI for Neulasta in the EU market.

The source population will be the primary person responsible for monitoring the OBI after application by the HCP, ie, patients or, if appropriate, their caregivers. This person will be defined as the "respondent". For every patient receiving OBI for Neulasta, the respondent will be defined at the time of study inclusion. In case the caregiver is identified as the respondent, the caregiver will need to be present at the time of OBI application and study inclusion.

Participating HCPs will assess the eligibility of respondents in a consecutive manner according to the date of OBI application. This approach is designed to minimise selection bias and to allow for the study results to be generalizable to the wider population of OBI treated patients. Upon patient and respondent consent to participate in the study, the HCP will immediately record in the study electronic case report form (eCRF) the information of the time and day of OBI application. Respondents will be contacted from approximately 27 to 72 hours after the OBI application (ie, approximately 0 to 45 hours after the Neulasta dose is expected to be delivered through the OBI) and asked to respond to a questionnaire. The questionnaire will be administered either by paper or online. Additionally, HCPs will be requested to provide data on their observations (eg, time and date of OBI administration, medication errors at the time OBI application, etc.) at each application of OBI for a participating patient in the eCRF.

Respondents can be included in the study multiple times at different chemotherapy cycles in which the OBI is being prescribed to the patient, if eligibility criteria including informed consent are met (Section 9.2.3). In subsequent administrations of the questionnaire, data will only be collected to meet the primary objective regarding medication errors (via a partial respondent questionnaire).

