Awareness of key safety messages and behavioural intent to carry out recommended actions as described in the PAC: will be evaluated using a set of multiple choice questions included in the questionnaire. A composite score for each individual will be calculated based on the proportion of all awareness and behavioural intent questions with correct responses.

The secondary endpoints for the respondent questionnaire are:

- Receipt of the PAC by the respondent: a categorical variable will describe if the respondent received the PAC.
- Medication errors with OBI administrations. The proportion of total OBI administrations with medication errors with respect to total OBI administrations, and the total number of patients will be calculated.

Measure of Success

The results of the study will be interpreted considering an acceptable level of patients and/or caregivers awareness and behavioural intent. The study estimates and associated 95% confidence intervals (CIs) will be evaluated in the context of a desired population-level threshold of at least 70%. The selection of a threshold for success is subjective and not based on a priori knowledge, experience, or established scientific criteria in the education or risk communication or evaluation literature. Therefore, the results will be contextualised with other available information. The appropriateness of the minimum 70% threshold as a measure of success will be reviewed at the time of the 1-year interim analysis.

Table 1. Measures of Success

Description of measure	Assessment
Distribution of the PAC	The threshold of 70% is within the 95% CIs of the proportion of respondents who provide an affirmative response to the key question regarding receipt of the PAC.
Success of the PAC	For the respondents who have received the PAC, the threshold of 70% is within the 95% CIs of the composite score for awareness and behavioural intent

Date: 10 April 2019 Page 23 of 61

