9.4 Data Sources

Data for this study will be collected through a questionnaire developed for the primary person responsible for monitoring the OBI after application (ie, patients or, if appropriate, their caregivers). Responses will be collected either by **paper** or online.

The questionnaire has been developed following standard questionnaire principles (Bowling, 2014). It will mainly include multiple choice questions with limited free text fields.

In addition, an eCRF for the HCP will be used to collect descriptive information about the HCP and site, information about the time and date of OBI administration, and of events related to medication errors.

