9.6 Data Management

As specified in Section 9.4 above, study data will be collected through two different sources:

- A respondent questionnaire developed to collect information from the primary person responsible for monitoring the OBI after application (ie, patients or, if appropriate, their caregivers). Responses will be collected either by paper or online.
- An eCRF for the HCP will be used to collect descriptive information about the HCP and the site, information about the time and date of OBI administration, and of events related to medication errors.

Upon inclusion of a new respondent **in**to the study (and after obtaining patient and respondent consent), the **HCP** will be asked to immediately complete information requested in the eCRF (ie, identification if the respondent is the patient or the caregiver, inclusion and exclusion criteria, and information of the current OBI application - medication errors and time and date of administration). The eCRF will subsequently generate a unique patient and respondent code (eg, UK-01-01-01). This code will be manually added to the ICF of the respondent by the **HCP** for reference purposes.

The HCP will give the respondent an envelope containing the instructions about how to complete the questionnaire (two options will be provided in the same envelope):

- a) Option 1. A document with the link to complete the questionnaire online.
- Option 2. Pre-paid and pre-filled envelope containing a paper copy of the respondent questionnaire and instructions for delivery to IQVIA to perform data entry.

The HCP will be subsequently responsible for conducting a telephone follow-up with the respondents to remind them about respondent questionnaire completion, within the timeframe established by the study protocol (ie, 27-72h post OBI application). For both options provided for questionnaire completion, the respondent will be initially requested to include the information on the respondent code (as provided by the HCP in the copy of the ICF, eg, UK-01-01-01), then respondent will be able to complete the rest of the questionnaire.

Date: 10 April 2019 Page 26 of 61

In case respondent completes the electronic questionnaire online, IQVIA will ensure that no contact information (eg, IP address, email, etc.) is recorded or captured in the corresponding database.

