9.7 Data Analysis

9.7.1 Planned Analyses

The statistical analysis will be conducted with SAS® statistical software or R. A detailed statistical analysis plan (SAP) will be prepared and accepted before the data analysis initiation.

All the respondents participating in the study who meet the eligibility criteria will be included in the sample of respondents in which reception of the PAC, awareness of key safety messages and behavioural intent to carry out recommended actions as described in the PAC will be assessed. Respondents monitoring more than one OBI application in the context of the study will complete reception of PAC, awareness of key safety messages and behavioural intent sections only for the first OBI application

Date: 10 April 2019 Page 29 of 61

All OBI applications reported by participant respondents will be included in the sample of treatments to estimate the proportion of OBI applications associated with medication error. OBI applications for Neulasta doses that have not been delivered (due to medication error) will be also included in the full analysis set of OBI applications. More than one OBI application can be reported for the same respondent.

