9.7.2.3 Descriptive Analysis

9.7.2.3.1 Description of Study Enrollment

A description of the number and percentage of respondents and OBI applications will be reported:

- Study population: All respondents invited to participate in the study.
- Eligible set: All respondents included in the study population who fulfill all selection criteria. Detailed information about eligible criteria not fulfilled will be also reported.
- Enrolled set: All respondents included in the eligible set who accept to participate in the study or who sign the informed consent.
- Full analysis set of respondents: Will include all respondents enrolled in the study
 who complete the questionnaire corresponding to at least one OBI administration
 and have valid responses to allow for the assessment of the primary objective.
- Full analysis set of OBI administrations: Will include all OBI administrations
 monitored by respondents included in the full analysis set of respondents and for
 which the corresponding questionnaire is completed and allows for the
 assessment of the primary objective.

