Device issues identified during OBI administration and subsequent events will be used to identify medication errors. Medication errors will be coded using the Medical Dictionary for Regulatory Activities (MedDRA) version 20 or later and analysed using the medication error Standardised MedDRA Query (SMQ). Subject incidence proportions of medication errors will be summarised. Medication errors will also be presented with respect to the total number of OBI administrations. The subgroups of initial and subsequent OBI applications will be analysed separately to assess the potential impact of subsequent administrations. If differences are not observed, the incidence of medication errors will be reported at overall level. If differences are observed, both subgroups will be separately reported.

Exploratory

The proportion of device issues at the time of OBI application (as reported by the HCP) will be reported at OBI administration and patient level.

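### The medication-error proportion is limited to administrations with a completed questionnaire, and the protocol does not fix whether errors recorded by the HCP count

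*Protocol*

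**What the plan says.** The protocol describes the population for the medication-error proportion in two ways.

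- **All administrations.** Section 9.3.2 defines the endpoint as "The proportion of total OBI administrations with medication errors with respect to total OBI administrations". Section 9.7.1.2 has the main analysis include every administration that meets the selection criteria.
- **Administrations with a questionnaire.** On the error estimate, section 9.7.1 says "All OBI applications reported by participant respondents will be included in the sample of treatments to estimate the proportion of OBI applications", and the abstract repeats this. Section 9.7.2.3.1 limits the full analysis set of OBI administrations to those for "which the corresponding questionnaire is completed and allows for the" assessment of the primary objective.

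It is also unclear which source supplies the errors. Section 9.3.2 introduces the endpoint under "The secondary endpoints for the respondent questionnaire are". Section 9.7.2.4 identifies errors from device issues during administration and from later events, and names no source.

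The HCP collects errors too. Section 9.1 asks HCPs to enter "medication errors at the time OBI application, etc.) at each application of OBI for a participating patient in the eCRF". Section 9.4 lists in the eCRF "information about the time and date of OBI administration, and of events related to medication errors", and section 9.6 has the HCP enter at inclusion "information of the current OBI application - medication errors and time and date of administration". Section 9.6.2 links the eCRF and the questionnaire by patient, respondent and administration. The only analysis expressly given to HCP-reported issues is the exploratory proportion of device issues at application (section 9.7.2.4).

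Section 9.9.4 expects a raised risk of non-response because of the 27 to 72 hour window. Section 9.7.2.2 rules out imputation and section 9.7.2.5 plans no sensitivity analysis.

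**The concern.** Section 7.2 gives measuring the medication-error rate as a reason for the study, following regulatory review. Under the analysis-set definition, an error that the HCP has already documented disappears from that estimate if the respondent does not return the questionnaire. If the questionnaire is returned but the respondent did not see or report the error, nothing in the protocol settles whether the HCP's record counts. Two analysts could follow the text faithfully and obtain different proportions.

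Few errors are expected, so one or two cases handled differently would change the result visibly. With no imputation and no sensitivity analysis, the report would not show how far the estimate depends on return of the questionnaire.

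**Working it through.** **Inputs from the protocol**
- Planned applications (section 9.5): 80 × 3.5 = 280, stated as a maximum. The figure reproduces.
- Illustrative true rate p (section 7.1): 5 unsuccessful of 297 administrations in healthy subjects, 5/297 = 1.68%. These are delivery failures, not coded medication errors. The same section reports medication errors in 0 of 262 subjects (pegfilgrastim) and 1 of 339 (placebo). The 1.68% serves only to show scale.
- Expected errors: 280 × 0.01684 = 4.7.

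**Assumptions (the protocol gives no figure)**
- r1, r0: questionnaire return rates for administrations with and without an error.
- f: share of errors recorded only by the HCP.

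**Mechanism 1: questionnaire not returned.** The administration leaves numerator and denominator together, so

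observed = p·r1 / (p·r1 + (1 − p)·r0).

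| r1 | r0 | Observed, p = 1.68% |
|---|---|---|
| 0.8 | 0.8 | 1.68% |
| 0.6 | 0.6 | 1.68% |
| 0.6 | 0.8 | 1.27% |
| 0.4 | 0.8 | 0.85% |
| 0.8 | 0.6 | 2.23% |
| 0.9 | 0.6 | 2.50% |

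For example, with r1 = 0.6 and r0 = 0.8: 0.01010 / (0.01010 + 0.78653) = 1.27%. With equal return, 0.9 to 1.9 of the 4.7 expected errors drop out, yet the proportion does not move. At p = 5% the unequal cases give 2.6% to 3.8% and 6.6% to 7.3%.

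**Mechanism 2: questionnaire returned, HCP-only error not counted.** The administration stays in the denominator, so observed = p·(1 − f).
- f = 0.2: 1.68% × 0.8 = 1.35%.
- f = 0.4: 1.68% × 0.6 = 1.01%.
- At p = 5%: 4.0% and 3.0%.

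This one can only lower the estimate. If all 280 questionnaires were returned, each such error would cost 1/280 = 0.36 percentage points.

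**Check on the obvious remedy.** Suppose the main denominator became all eCRF-recorded applications, and a non-returned application counted as error-free unless the HCP saw an error. With return rate r unrelated to error, observed = p·(f + (1 − f)·r). For f = 0.2 to 0.4 and r = 0.6 to 0.8 this gives 1.14% to 1.48%, against a true 1.68%. The eCRF is completed at identification and consent (section 9.3), while delivery starts 27 hours after application (section 7.1), so it cannot record later failures.

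**Bounds.** At 80% return, 224 of 280 are analysed and 56 are not. Expected errors among the 224 are 224 × 0.01684 = 3.77. With none of the 56 an error: 3.77/280 = 1.35%. With all 56 an error: (3.77 + 56)/280 = 21.3%.

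**The case against.** A reader might infer that medication errors are counted only from questionnaires. The text does not go that far. The restriction to completed questionnaires is firm for the analysis set, but section 9.7.2.4 names no source for the numerator and section 9.6.2 plans the linkage that would let eCRF errors be counted. Reporting HCP device issues in an exploratory table does not exclude them from the error count.

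A reader might also infer that the proportion must be too low, for instance by taking lost errors off a fixed denominator of 280. An unreturned questionnaire removes the application from the denominator as well, so the direction depends on whether return differs after an error. Higher return after an error is conceivable: the Patient Alert Card tells patients with a device issue to call their healthcare professional at once, and the HCP also makes the reminder calls (section 9.6).

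Nor do the documents show that respondents miss errors at application. A caregiver respondent must be present (section 9.1), and a patient respondent necessarily is. Of the three frequent post-marketing terms in section 7.1, two (dose omission and underdose) concern failures whose signs the card teaches respondents to recognise, and nothing says the third, wrong technique, refers to the HCP's technique. The HCP data are not wholly lost, and the counts by analysis set will show the shortfall in questionnaires.

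All of this stands. It leaves untouched the conflict between the two populations, the loss of documented errors without a questionnaire, and the unsettled numerator. The analysis set is fixed in the protocol itself, so this is more than a detail left to the SAP.

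**Conclusion.** The point holds in a limited form. The protocol restricts the medication-error proportion to administrations with a completed questionnaire, against its own definition over all administrations, and does not settle whether HCP-recorded errors count among those that remain.

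The estimate may be biased. The direction is certain only if HCP-only errors are left out where a questionnaire was returned, which the protocol neither states nor excludes. Bias through non-return can go either way or be absent. A general claim of underestimation is not supported.

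Every size given rests on the illustrative 1.68% and on assumed return rates and HCP-only shares. With about 4.7 errors expected in at most 280 applications, the unsettled choices could change the reported rate by a third or more in relative terms in several of the cases shown. The matter should be corrected; it does not threaten the primary objective.

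**What to change.** 1. Define a medication error as one identified from either the eCRF or the respondent questionnaire, counted once per application, and say so in sections 9.3.2 and 9.7.2.4.
2. Reconcile sections 9.3.2 and 9.7.1.2 with sections 9.7.1 and 9.7.2.3.1, and keep the questionnaire-completed set as the main denominator. The tie to the primary objective in section 9.7.2.3.1 needs correcting at the same time, because the partial questionnaire used at later cycles does not collect awareness or intent (section 9.3).
3. Report the number of eCRF-recorded errors that have no questionnaire.
4. Add one sensitivity table over all eCRF-recorded applications of consented patients, with best-case and worst-case bounds for non-returned applications. Non-returned applications should not simply be treated as error-free unless the HCP saw an error, since that understates the rate.

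The cost is revised wording and one table. Both data sources and the link already exist. The downsides are that non-returned applications rest on what the HCP saw at application only, and that the worst-case bound will be wide if return is poor.

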9.7.1.1 Interim Analysis/Analyses

An interim analysis is planned to be implemented at 1 year after start of data collection. All respondents and OBI applications available at time of analysis will be included. All descriptive tables planned for the final analysis will be also performed in the interim analysis. The appropriateness of the minimum 70% population-level threshold established as the measure of success for the distribution of the PAC and for the awarereness and behavioural intent to carry out recommended actions in the PAC will be reviewed at the time of the 1-year interim analysis, and addressed if required.

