9.7.1.2 Primary Analysis

The primary analysis will be performed at the end of data collection including all respondents and OBI administrations fulfilling selection criteria. All statistical analyses planned in the SAP approved prior to initiation of the statistical analysis will be performed.

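### The 70% success threshold may be reviewed and revised at the interim that produces every outcome table, so the Table 1 verdict can be shaped by the study's own data

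*Protocol*

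**What the plan says.** Section 9.3.2 of the protocol (Measure of Success) sets a "desired population-level threshold of at least 70" per cent. Table 1 turns it into two verdicts, one on distribution of the Patient Alert Card (PAC) and one on its success. The second is met, among respondents who received the card, when "the threshold of 70% is within the 95% CIs of the composite score for awareness and behavioural intent". The first applies the same rule to the proportion who report receiving the card.

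The protocol is open about the basis of the figure: "The selection of a threshold for success is subjective and not based on a priori knowledge, experience". It then adds: "The appropriateness of the minimum 70% threshold as a measure of success will be reviewed at the time of the 1-year interim analysis".

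Section 9.7.1.1 repeats this for both success measures and goes one step further: the threshold "will be reviewed at the time of the 1-year interim analysis, and addressed if required". On the content of that interim it says "All descriptive tables planned for the final analysis will be also performed in the interim analysis", and on its population "All respondents and OBI applications available at time of analysis will be included". Section 9.7.1.2 then states: "The primary analysis will be performed at the end of data collection including all respondents and OBI administrations fulfilling selection criteria". Respondents seen at the interim are therefore part of the final verdict.

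**The concern.** A success threshold protects a conclusion only if it is fixed without knowledge of the results it will judge. Here one step at one year both displays the outcomes and reopens the threshold. The protocol gives no criterion for a change and no limit on its direction or size. It does not order the review before the tables or keep it blind to them, and it does not require the final result to be stated against the original 70%. Because no external basis is given for 70%, the interim results are the most obvious new information by which its appropriateness could be judged.

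At stake is the success label. Section 9.7.2.4 says the study will help indicate, through the assessment in 9.3.2, whether the PAC works as a risk minimisation measure, and section 13 sends the final report to the Pharmacovigilance Risk Assessment Committee (PRAC).

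**Working it through.** **Inputs from the protocol.** Threshold 70% and the rule that it lies within the 95% CI (Table 1); about 80 respondents (9.5); normal-approximation CI (footnote to Table 2).

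**Assumptions, since the protocol gives no values.** Alternative threshold 60%; 40 respondents at the interim, with a range of 30 to 50.

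**The plan's own figure.** The half-width is 1.96 × √(p(1−p)/n). For p = 0.7 and n = 80 it is 1.96 × √(0.21/80) = 0.1004, and Table 2 gives 0.10. All 15 cells of Table 2 reproduce to two decimals.

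**Which results pass at n = 80.** The threshold must lie between x/80 minus and x/80 plus the half-width.

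- Threshold 70%, lower end: 47 of 80 gives 0.5875 + 0.1079 = 0.695 (fails); 48 of 80 gives 0.6000 + 0.1074 = 0.707 (passes).
- Threshold 70%, upper end: 63 of 80 gives 0.7875 − 0.0896 = 0.698 (passes); 64 of 80 gives 0.8000 − 0.0877 = 0.712 (fails as literally worded). The band is 48 to 63.
- Threshold 60%, lower end: 39 of 80 gives 0.4875 + 0.1095 = 0.597 (fails); 40 of 80 gives 0.5000 + 0.1096 = 0.610 (passes).
- Threshold 60%, upper end: 56 of 80 gives 0.7000 − 0.1004 = 0.5996 (passes). The band is 40 to 56.

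Results of 40 to 47 of 80 (50% to 58.75%) change from failure to success.

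**Chance of meeting Table 1's rule, threshold fixed throughout.** Sum the binomial probabilities C(80,x) p^x (1−p)^(80−x) over each band:

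| True level | Threshold 70% | Threshold 60% |
|---|---|---|
| 50% | 4.6% | 54.4% |
| 55% | 21.6% | 84.2% |
| 60% | 54.8% | 94.8% |

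**Threshold lowered in response to the interim.** Suppose it drops to 60% only when the interim upper CI limit is below 70%. With 40 at the interim this happens at 21 of 40 or fewer: 0.525 + 0.155 = 0.680, whereas 22 of 40 gives 0.550 + 0.154 = 0.704. Multiply the binomial probabilities of the interim count and of the later count, and sum over all pairs whose total passes at the threshold then in force:

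| True level | Fixed at 70% | 30 at interim | 40 at interim | 50 at interim |
|---|---|---|---|---|
| 50% | 4.6% | 25.2% | 30.8% | 42.7% |
| 55% | 21.6% | 43.8% | 49.8% | 64.5% |

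The binomial calculation fits PAC receipt directly. The composite score is a mean of per-respondent proportions, so its CI may be narrower, and its denominator is only those who received the card. For that measure the figures are illustrative.

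**The case against.** The best defence is that this is a descriptive study. Section 7.3 rules out hypothesis testing, estimates and CIs are reported whatever the threshold, and any reader can set them beside 70%. Section 9.3.2 admits that the threshold is subjective and promises to put the results in context. Under 12.1 amendments need ethics approval, and under 13 the study is registered before data collection, so a change would probably be visible. Section 9.7.2.4 also keeps a 70% cut-off for the categorised composite score. All of this limits the damage to the success label, but none of it prevents the label from being set with outcome data in hand. Nor does acceptance of the statistical analysis plan before data analysis (9.7.1), because the protocol itself places the review at the interim.

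A reader might infer more than the text supports:

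- **That the threshold will be changed after the tables have been read.** The protocol speaks of review at the time of the interim and of addressing the matter if required. A later change is a natural reading, and nothing excludes it, but it is not stated. The threshold could also be raised.
- **That this is type I error inflation, or that the final results lose all evidential value.** There is no test and no alpha, and the estimates and CIs remain valid.
- **That the move to 60% raises success from 4.2% to 54.8% at a true 60%.** Those figures ask whether the point estimate reaches the threshold. Under Table 1's CI rule the pair is 54.8% and 94.8%.
- **That the threshold would be reset to the interim estimate, making the verdict nearly independent of the truth.** Nothing in the protocol proposes this, and the result depends heavily on the interim count. That count may be well below half, because launches are staggered and sites may be added (9.2, 9.2.1).

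**Conclusion.** The point holds for the success verdict. The protocol lets the threshold be revised at the same interim that displays the outcomes, and it has no safeguard that keeps the original 70% in force. If the threshold moved to 60%, the chance of success at a true level of 50% would rise from 4.6% to 54.4%. If it were lowered only after a clearly poor interim, the chance would rise to about 31% (25% to 43% for 30 to 50 respondents at the interim). These sizes rest on the assumed 60%, the assumed interim counts, 80 final respondents and a binomial CI.

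One separate matter affects the arithmetic. Read literally, Table 1 also fails results of 64 of 80 or more, because their whole CI lies above 70%. The comparisons at true levels of 50% and 55% are hardly touched by this, since such results are rare there.

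**What to change.** In 9.3.2 and 9.7.1.1, state three things:

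1. The verdict against the original 70% is always reported, for both measures in Table 1.
2. Any revised threshold is shown only as an additional descriptive benchmark, with its reason and date.
3. Any review of the threshold rests on information from outside the study and is completed before interim outcome tables are produced.

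This is about one sentence in each section and needs no extra respondents, data or time. The cost is that the sponsor can no longer replace a threshold that it calls subjective. It can still explain in the report why another value might be more suitable.
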